4.5.8.2 Electrocardiogram

Summaries for ECGs will be presented for ventricular rate, PR interval, QRS duration, mean QT duration (overall, and for males and females separately) and QTcB (overall, and for males and females separately), at each visit. Change from baseline to each post-baseline visit will also be presented.

Based on the criteria presented in Section 6, defined flagged values will be identified at each visit. The number of patients with at least one post-baseline flagged ECG parameter value will be summarized by parameter and flagged criteria.

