4 EXPERIMENTAL PLAN

4.1 Study Design

This is a multi-center, OLE study for patients with DS or LGS who have completed the double-blind, placebo-controlled, clinical studies of GWP42003-P (Core Studies). The study consists of a titration period and a maintenance period, followed by a 10-day taper period.

Titration Period: All patients will titrate up to 10–20 mg/kg/day GWP42003-P using a recommended titration schedule (see [APPENDIX 4](#)). It is advised that the Investigator considers monitoring hepatic function (alanine aminotransferase [ALT], aspartate aminotransferase [AST], total bilirubin [TBL] and international normalized ratio [INR] levels) during the titration period for patients taking concomitant AEDs that are known to be associated with hepatic injury or failure. To minimize any elevations in hepatic function markers the titration period can be extended and the dosage of a concomitant AED and/or GWP42003-P may be adjusted at the discretion of the Investigator. If there is intolerance during titration, the patient may be maintained on a dose below 10–20 mg/kg/day. A titration rate faster than recommended may be considered if there is an increase in seizures, following consultation with the GW medical monitor.

Maintenance Period: Patients will continue dosing at 10–20 mg/kg/day. However, Investigators may decrease the dose if the patient experiences intolerance, or increase the dose if required for better seizure control, until the optimal dose is found. The Investigator may schedule additional clinic visits to facilitate dose adjustments e.g., when increasing doses above 20 mg/kg/day. Patients whose dose has been decreased can have their dose increased again provided there is adequate tolerance. The maximum dose patients can receive will be 30 mg/kg/day (51 mg/kg/day is the maximum dose safely used in the USA EAP to date with a mean dose of 24 mg/kg/day [$n = 59$]). Dose increases above 20 mg/kg/day are recommended to be done slowly, with maximum increments of 2.5 mg/kg every 5–7 days. If seizure freedom is achieved with use of GWP42003-P during the study, the Investigator can consider reducing the dose of concomitant AEDs after consultation with the GW medical monitor.

Study Completion: The maximum duration of this OLE study will be 4 years (208 weeks after Visit 1).

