4.1.1.1 Choice of Baseline

For all visit-based endpoints, change from baseline will be calculated with reference to the core study baseline only.

For seizure-related endpoints, percentage change from baseline will be calculated from the core study baseline period.

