4.4.4 Demographic Data and Baseline Characteristics

The following demographic data will be summarized:

- Age (years);
- Age group (2-5 years, 6-11 years, 12-17 years and 18-55 years);
- Sex;
- Race;
- Country;
- Region (US, Rest of the World);
- Weight at Visit 1 (kg);
- Height at Visit 1 (cm);
- Body mass index at Visit 1 (kg/m²).

Age will be calculated as:

$$(\text{Date of Visit 1} - \text{date of birth}) \div 365.25$$

The following baseline characteristics will be summarized by indication and overall:

- Number of AEDs a patient is currently taking.
- Number of patients taking clobazam (Yes, No).
- Number of patients taking valproic acid (Yes, No).
- Number of patients taking lamotrigine (Yes, No).
- Number of patients taking levetiracetam (Yes, No).
- Number of patients taking rufinamide (Yes, No).
- Number of patients taking topiramate (Yes, No).
- Number of patients taking felbamate (Yes, No).

The number of AEDs a patient is currently taking is based on the 'Concomitant antiepileptic medications' CRF page. Patients taking the same AED type, but where the AED were coded to different generic terms will be counted only once within the AED type. For example, valproate sodium, valproic acid, valproate semisodium and ergenyl chrono will all be counted as valproic acid and counted once under that term.

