Appendix 3 Defined Flagged Values in ECG Parameters

Defined flagged values that will be used to identify low or high ECG parameters (See Section 4.5.8.2) are presented in Table 9.

Table 9 Defined Flagged Values for ECG Parameters

ECG Parameter	Flag
QTc	> 450, > 480, > 500

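### QTcB is the only rate-corrected QT in the plan and Table 9 has no increase-from-baseline category, so QTc change is confounded with heart rate; adding QTcF and increase categories is a cheap improvement

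*SAP*

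**What the plan says.** ECG change relative to the core study baseline is part of the primary safety endpoint (Protocol 4.1.1; SAP 3.3.1). SAP 4.5.8.2 sets out the summaries: "Summaries for ECGs will be presented for ventricular rate, PR interval, QRS duration, mean QT duration", followed by "QTcB (overall, and for males and females separately". It adds: "Change from baseline to each post-baseline visit will also be presented". The baseline is fixed in SAP 4.1.1.1: "For all visit-based endpoints, change from baseline will be calculated with reference to the core study baseline only". Neither document names any rate correction other than QTcB.

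The only ECG parameter with flag limits is QTc (SAP Appendix 3, Table 9): "> 450, > 480, > 500". The table does not name the correction, sets no limit on change and has no age-specific limits. Counting is per patient over the whole post-baseline period: "The number of patients with at least one post-baseline flagged ECG parameter value will be summarized by parameter and flagged criteria". By contrast, Appendix 2, Table 7 does set change criteria for blood pressure, pulse (more than 15 in either direction) and weight.

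On population and follow-up, the SAP uses the bands "Age group (2-5 years, 6-11 years, 12-17 years and 18-55 years" (4.4.4), and Protocol 4.1 states: "The maximum duration of this OLE study will be 4 years (208 weeks after Visit 1". The study is single-group (Protocol 7.1).

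**The concern.** Bazett's formula divides QT by the square root of the RR interval. If QT shortens less steeply than that as heart rate rises, QTcB reads high at fast rates and loses that excess when the rate slows. Three of the four age bands are below 18 years, and a patient may be compared with a baseline taken years earlier. A drift in heart rate between baseline and a later visit would then appear as a change in QTcB, and no concurrent arm is available to show that the drift comes from heart rate.

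Two outputs are affected. The mean change in QTcB could understate a real increase if rate falls, or suggest an increase if rate rises. The ever-flagged counts could include patients whose QTcB is high only because their rate is fast. Without an increase category, the counts also do not separate a patient who was already above 450 at baseline from one who became so on treatment.

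**Working it through.** The plan states no ECG rate, heart rate or QTc value, so there is no figure of its own to reproduce. The check is algebra with declared assumptions.

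**Inputs**
- QTcB = QT / RR^0.5, with RR = 60/HR in seconds (HR in bpm).
- Assumed relation: QT = Q0 × RR^b, where Q0 is the rate-independent QTc.
- Q0 = 410 ms (assumption).
- b = 1/3, the Fridericia exponent, as the main case; range 0.30 to 0.42, with 0.5 as the limit where Bazett is exact (assumptions).
- Shift of 15 bpm, from the pulse-change criterion in SAP Table 7. The starting point of 100 bpm is the upper pulse flag in SAP Table 8. That patients' rates move between 100 and 85 bpm is an assumption.
- Table 9 limits are read as milliseconds.

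**Formula.** Substituting gives QTcB = Q0 × (HR/60)^(0.5 − b). It is free of heart rate only if b = 0.5.

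**Level of QTcB with Q0 = 410 and b = 1/3**
- 80 bpm: 410 × (80/60)^(1/6) = 430.1 ms
- 85 bpm: 434.5 ms
- 100 bpm: 446.4 ms
- 120 bpm: 460.2 ms

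**Change in QTcB with no true change, 100 to 85 bpm**

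| b | QTcB at 100 bpm | QTcB at 85 bpm | Change (ms) |
|---|---|---|---|
| 0.30 | 454.1 | 439.6 | −14.5 |
| 1/3 | 446.4 | 434.5 | −11.9 |
| 0.38 | 435.9 | 427.5 | −8.4 |
| 0.42 | 427.1 | 421.6 | −5.5 |
| 0.50 | 410.0 | 410.0 | 0 |

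A rise from 85 to 100 bpm gives the same figures with a plus sign.

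**True increase that would show as zero.** For QTcB to stay at 446.4 ms after a fall to 85 bpm with b = 1/3, Q0 must rise to 410 × (100/85)^(1/6) = 421.3 ms. A true increase of about 11 ms would be cancelled.

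**Worked patient.** With b = 1/3, suppose the true QTc rises from 420 to 430 ms while heart rate falls from 110 to 85 bpm. QTcB goes from 464.6 to 455.7 ms: a true rise of 10 ms appears as a fall of about 9 ms. The patient is above 450 at both times.

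**Heart rate at which an unprolonged 410 ms patient crosses 450.** HR = 60 × (450/410)^(1/(0.5 − b)): 95.6 bpm at b = 0.30, 104.9 at 1/3, 130.3 at 0.38 and 192.1 at 0.42. False flags thus depend strongly on the exponent.

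**QTcF under the same model.** QTcF = Q0 × (HR/60)^(1/3 − b). For 100 to 85 bpm its change with no true change is −2.3 ms at b = 0.30, 0 at 1/3, +3.0 at 0.38, +5.6 at 0.42 and +10.3 at 0.5. Near 0.42 the two corrections err by about the same amount in opposite directions.

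**The case against.** A reader might infer that ECG safety rests on Bazett QTc alone. The SAP does not support that. Ventricular rate, PR, QRS and uncorrected QT are also summarised by visit with change from baseline, ECG data are listed (Listings 14.3.1 and 14.3.2), and Protocol 9.1.8 requires a physician to review each ECG and record relevant abnormal findings. A shift in heart rate would be visible beside the QTcB change. What remains is that separate group summaries of QT and of rate cannot be recombined into a within-patient rate-corrected change.

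A reader might also infer that prolongation will be hidden. That direction is conditional. It needs heart rate to fall, and the documents report no heart rates; a rise reverses the sign, and the growth argument does not apply to the 18–55 band. For absolute flags, Bazett errs towards over-flagging above 60 bpm. Missing a case needs a rate below 60: at 50 bpm with b = 1/3, QTcB reaches 450 only when the true QTc is 464 ms.

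The size rests on the exponent, and nothing in the documents says which one fits these patients. Four years is a maximum: SAP Table 2 (4.1) shows that some patients completed after one year. Table 9 says only QTc, so its reading as QTcB is inferred from there being no other QTc in the SAP.

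Finally, all analyses are descriptive, and no QTc value appears among the withdrawal criteria (Protocol 10). These points limit the consequence but do not remove the confounding.

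**Conclusion.** The point holds as a cheap improvement. QTcB is the only rate-corrected QT, its change is always taken from the core study baseline, and Table 9 neither names its correction nor includes any increase category. If the exponent is below 0.5, change in QTcB is confounded with heart rate. For a shift between 100 and 85 bpm the artefact is about 12 ms at an exponent of 1/3, 5.5 to 14.5 ms over 0.42 to 0.30, and zero at 0.5, in whichever direction the rate moves. A bias towards no prolongation follows only if rate falls as children grow. Flags at fast rates would give mainly false positives, above about 105 bpm for a 410 ms patient at exponent 1/3. All of this rests on assumed values for heart rate, exponent and true QTc.

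The documents give no basis for replacing QTcB by QTcF as the main measure, since QTcF is not exact either. They do support reporting both.

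**What to change.** - Derive QTcF for each patient and visit, including the core study baseline, from the recorded QT and ventricular rate. Report it alongside QTcB in the visit summaries, change from core study baseline and flag counts (Tables 14.2.1 and 14.2.2).
- State in Table 9 which correction each QTc flag uses.
- Add increases from core study baseline of > 30 and > 60 ms to Table 14.2.2, for both corrections.
- Correct the cross-reference in SAP 4.5.8.2: it points to Section 6 for the flag criteria, but Section 6 is the reference list and the criteria are in Appendix 3.

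The cost is analysis only: both inputs are already collected and summarised. The downside is a few more table rows and two corrections that may differ. Where they do, the ventricular rate summary should be read beside them.

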4. STATISTICAL METHODS

4.1 General Considerations

All tables will be presented by indication (where appropriate), including an overall count, as follows:

Dravet Syndrome (N=XX)	Lennox-Gastaut Syndrome (N=XX)	Overall (N=XX)
------------------------	--------------------------------	----------------

In all tables, listings and figures, the study visits will be referred to and labelled as per [Table 2](#)

Table 2 Study Visits

Actual Visit	Visit Label
Visit 1: Day 1	Day 1
Visit 2: Day 15	Day 15
Visit 3: Day 29	Day 29
Visit 4: Day 85	Day 85
Visit 5: Month 6 or Week 24	Week 24
Visit 6: Month 9 or Week 38	Week 38
Visit 7: Week 48 or End of Treatment (only patients who completed at 1 year)*	Week 48
Visit 8: Week 76	Week 76
End of Treatment (only patients who completed on or after Day 400)*	End of Treatment

End of Treatment (withdrawn patients only)	End of Treatment
End of Taper	End of Taper
Post-Taper Safety Call	Post-Taper Safety Call
Safety Follow-Up	Safety Follow-Up

* For some patients, the end of treatment visit occurs after one year in the OLE, whereas for other patients the end of treatment visit occurs after two or more years in the OLE.

Unless stated otherwise, continuous variables will be summarized showing the number of non-missing values (n), mean, standard deviation, median, minimum and maximum and categorical variables will be summarized showing the number and percentage of patients falling in each category. For continuous summaries of seizure frequency, the lower and upper quartiles will also be presented.

Minimum and maximum values will be presented to the same decimal precision as the raw data. Mean and median will be presented to one more decimal place than the raw data, and standard deviation to 2 more decimal places than the raw data. Percentages will be presented to one decimal place.

For patients who enter the OLE on the same day as the core study end of treatment or end of taper visit, the CRF for this study did not require some data to be entered for a second time. Hence, for visit based endpoints, if a patient does not have data entered in this study at Visit 1, then data from the end of treatment or end of taper visit in the core study will be used, provided that the date of collection is on Day 1 of the OLE.

Unless otherwise stated, all summaries will be presented by indication.

All analyses and summaries will be produced using SAS Version 9.4.

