4.1.4 Definitions

4.1.4.1 Core Study Baseline

For interactive voice response system (IVRS) based endpoints, the core study baseline will include all available data prior to Day 1 of the core study as per the derivation in the core study.

For visit based endpoints, the core study baseline will be the visit that was assigned as baseline in the core study. No re-derivation will be carried out.

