4.5.1 General Approach

All endpoints will be summarized on the safety analysis set, unless specified otherwise. Endpoints will be summarized by indication including an appropriate overall summary, unless specified otherwise. Each individual endpoint section also describes any further categorization of the data above that described in this section.

Throughout this section, whenever change from baseline is referenced and the endpoint is non-seizure related the baseline that is used will be the core study baseline. Please refer to Section 4.5.9 for specific rules for the choice of baseline for seizure-related endpoints.

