4.5.3 Clinical Laboratory Evaluation

4.5.3.1 Hematology and Biochemistry

Summaries for hematology and biochemistry will be presented for each laboratory parameter at each visit. Change from baseline to each post-baseline visit will also be presented.

If values for any of the parameters are below or above the limit of quantification of the assay (BLQ or ALQ), then they will be included in the summary tables at the BLQ or ALQ thresholds.

For post-baseline visits where laboratory samples are repeated, the values from the first non-missing repeat sample taken for the visit, provided it is taken no more than 7 days after the initial sample, will be used. If no values from repeat samples taken within 7 days are available, then the results from the visit sample should be used.

Shift tables for hematology and biochemistry parameters will be constructed, based upon normal ranges and GW toxicity limits (See Section 6), to determine the categorical shifts from core study baseline to each post-baseline visit. Values will be categorized as 'Normal', 'Low' or 'High' based on normal ranges and 'Toxically Low', 'Toxically Normal' or 'Toxically High' based on GW toxicity limits.

An additional table will be produced, summarizing the number of patients with at least one incidence post-Visit 1 of potential Hy's Law case. Potential Hy's Law case is determined by any increase of alanine transaminase (ALT) or aspartate transaminase (AST) to ≥ 3 times the upper limit of normal (ULN) for patients with normal values at core study baseline (or ≥ 3 times core study baseline value for patients with elevated values at core study baseline) and to >2 times the ULN for patients with normal values at core study baseline (or >2 times baseline value for patients with elevated values at core study baseline) in total bilirubin.

All laboratory data will be listed; listings will include limited demographic information about the patient (age, sex, race and weight at core study baseline). Abnormal laboratory values will be listed separately. A further listing will be created for the laboratory reference ranges and toxicity limits.

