4.5.8 Vital Signs, Other Physical Findings and Other Safety Data

4.5.8.1 Vital Signs

All vital signs measurements are taken in a sitting position after five minutes of rest.

Summaries for vital signs (systolic blood pressure, diastolic blood pressure, pulse rate, temperature and respiratory rate) will be presented for each vital sign parameter at each visit. Change from baseline to each post-baseline visit will also be presented.

Based on the criteria presented in Section 6, clinically significant changes from core study baseline in vital signs measurements and other defined flagged values will be identified at each visit. The number of patients with a clinically significant change from core study baseline will be summarized by parameter and visit. The number of patients with at least one post-baseline flagged vital sign parameter value will be summarized by parameter and flagged criteria.

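### The ever-flagged vital-sign and ECG counts do not exclude OLE Visit 1 values, although the Hy's Law count does

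*SAP*

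**What the plan says.** SAP 4.5.8.1 counts vital-sign flags this way: "The number of patients with at least one post-baseline flagged vital sign parameter value will be summarized by parameter and flagged criteria". SAP 4.5.8.2 uses the same rule for ECG: "The number of patients with at least one post-baseline flagged ECG parameter value will be summarized by parameter and flagged criteria". These sentences feed Tables 14.1.3 and 14.2.2. Both sections identify flags visit by visit.

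The baseline is fixed in three places:

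- 4.1.1.1: "For all visit-based endpoints, change from baseline will be calculated with reference to the core study baseline only"
- 4.1.4.1: "For visit based endpoints, the core study baseline will be the visit that was assigned as baseline in the core study"
- 4.5.1: "whenever change from baseline is referenced and the endpoint is non-seizure related the baseline that is used will be the core study baseline"

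No separate OLE baseline is defined. SAP Table 2 lists OLE Visit 1 as a study visit labelled Day 1. When nothing was entered for Visit 1 in this study, SAP 4.1 says that "data from the end of treatment or end of taper visit in the core study will be used", if those data were collected on OLE Day 1.

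For liver safety, SAP 4.5.3.1 words the corresponding count differently: "number of patients with at least one incidence post-Visit 1 of potential" Hy's Law cases.

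**The concern.** An ever-flagged count in an open-label extension is normally read as what happened on extension treatment. Here the word post-baseline points back to the Core Study, so a Visit 1 reading qualifies even though Protocol 9.2.1 starts OLE dosing that evening. The flags are absolute thresholds (for example pulse above 100 or QTc above 450, SAP Appendices 2 and 3), so a value can be flagged with no change on treatment.

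What a Visit 1 value represents depends on the patient:

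- For a former placebo patient, it precedes any study GWP42003-P.
- For a former active patient, it is a Core Study on-drug or taper value, or an off-drug re-assessment if there was a dosing gap.

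Vital signs and ECG belong to the primary safety endpoint (SAP 3.3.1), and the ever-flagged tables do not separate these readings from later ones.

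**Working it through.** **1. Does the wording admit Visit 1?**

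| Rule | Where | Time limit |
|---|---|---|
| Ever-flagged vital signs | SAP 4.5.8.1 | post-baseline; baseline = Core Study |
| Ever-flagged ECG | SAP 4.5.8.2 | post-baseline; baseline = Core Study |
| Potential Hy's Law case | SAP 4.5.3.1 | post-Visit 1 |
| Treatment-emergent AE | SAP 4.5.2 | on or after first OLE dose |
| Physical findings recorded as AEs | SAP 4.5.8.3 | after Visit 1 |

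SAP 4.5.8.2 also uses the term just before the flag rule: "Change from baseline to each post-baseline visit will also be presented". There it must mean after the Core Study baseline. Nothing in either section gives it a narrower meaning for the flag count. The SAP does not state that Visit 1 is counted, but its definitions give no ground for leaving it out.

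**2. Is Visit 1 before the first OLE dose?** Under Protocol 9.2.1, yes: dosing starts that evening, and for same-day entrants the Core Study end-of-treatment vital signs and ECG serve as Visit 1 data. SAP 4.5.8.13 instead places the first dose in the clinic at Visit 1. Even then, values filled in under SAP 4.1 are Core Study measurements, and no rule restricts the flags to post-dose readings.

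**3. Former placebo share.** The randomized numbers in SAP Table 1, multiplied by the planned placebo fractions, give

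34/5 + 120/2 + 199/3 + 171/2 + 225/3 = 6.8 + 60 + 66.3 + 85.5 + 75 = 293.6 of 749, or 39.2%.

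If OLE entrants have the same mix, 39.2% of the planned 680 is about 267 patients.

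**4. Size.** The documents contain no figure to reproduce and no flag rates, so this is an illustration. Assume each visit has flag probability p, the same at Visit 1, and within-patient correlation rho (beta-binomial). With a = p(1−rho)/rho and b = (1−p)(1−rho)/rho, the share flagged at least once in k visits is

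1 − ∏ (b+i)/(a+b+i), for i = 0 to k−1.

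For rho = 0 this becomes 1 − (1−p)^k. Admitting Visit 1 changes k to k+1. SAP Table 2 gives k = 8 post-dose visits: Day 15, Day 29, Day 85, Weeks 24, 38, 48 and 76, and End of Treatment.

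For p = 5% and rho = 0.5, a = 0.05 and b = 0.95. Eight visits give 12.88%. The ninth factor is 8.95/9, and the share becomes 13.36%, a rise of 0.48 points. That is 680 × 0.48% = 3.3 patients per flag, of whom 267 × 0.48% = 1.3 are former placebo patients.

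Rise in the share ever flagged, in percentage points:

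| rho | k | p = 1% | p = 5% | p = 10% |
|---|---|---|---|---|
| 0.5 | 3 | 0.25 | 1.14 | 2.07 |
| 0.5 | 8 | 0.11 | 0.48 | 0.84 |
| 0.5 | 9 (End of Taper added) | 0.10 | 0.43 | 0.75 |
| 0.5 | 12 (full protocol schedule) | 0.07 | 0.33 | 0.56 |
| 0.7 | 8 | 0.05 | 0.23 | 0.42 |
| 0 (bound) | 8 | 0.92 | 3.32 | 4.30 |

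The k = 12 row counts Visits 2 to 12 plus End of Treatment (Protocol Appendix 1). The k = 3 row stands for patients who leave early. Independence between visits (rho = 0) is not plausible for stable patient traits and serves only as a bound for that visit count.

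**The case against.** The strongest reply is that this is loose wording and not a demonstrated error. The SAP never says that Visit 1 is counted, and the table shells or programming specification may exclude it. Protocol 13.6.2.3 calls OLE Visit 1 screening for these same data and lists it apart from the treatment period, so someone reading both documents has a reason to leave it out. The Core Study frame is also deliberate, because the primary endpoint is defined against that baseline. For former active patients, about 61% on the same estimate, a Visit 1 value is usually obtained on drug or during taper, so counting it in a long-term exposure summary is not plainly wrong. The AE and physical-finding rules govern event classification, which leaves Hy's Law as the only like-for-like comparator.

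Much of this is fair. The claim has to stay at does not exclude, and the effect is close to nil on plausible assumptions. However, the protocol's screening label does not define the flag counts, and the SAP does not carry it into them. If anything, it shows that Visit 1 was regarded as pre-treatment, which supports the change. The Core Study baseline is right for change scores, but that does not settle which visits belong in an ever-flagged count. The one close comparator is also the one where the authors wrote the limit out.

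**Conclusion.** The concern holds as a minor point. Read as written, the two ever-flagged counts admit OLE Visit 1 values that under the protocol precede OLE treatment, and any such inclusion can only raise them. At a correlation of 0.5 and 8 post-dose visits, the rise is about 0.1 to 0.8 percentage points for per-visit flag probabilities of 1 to 10%. It is larger for patients with few visits and smaller with more visits or stronger correlation. The flag probabilities, the correlation and the OLE placebo share are all assumptions. No hypothesis test depends on the two tables, and Visit 1 values can be traced in the by-visit summaries and in the vital-sign and ECG listings.

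**What to change.** In the flag-count sentences of SAP 4.5.8.1 and 4.5.8.2 (Tables 14.1.3 and 14.2.2), replace the word post-baseline with post-Visit 1 (after the first OLE dose), in line with the Hy's Law count in 4.5.3.1 (Table 13.4). Leave the Core Study baseline in place for the change-from-baseline summaries. The cost is one phrase in each of two sentences and one programming condition, with no new data. If the sponsor already intends to exclude Visit 1, the edit simply records that.
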